11.1 Primary and Secondary Endpoint Analyses

11.1.1 Primary Endpoint Analyses

The primary endpoint is the time-matched difference between the OPC-61815 and placebo data in change from baseline for QTcF in 12-lead Holter ECG. Central tendency analysis for OPC-61815 will be performed for subjects in the pharmacodynamic analysis set who appropriately completed all IMP treatments (OPC-61815 16 mg, OPC-61815 32 mg, placebo, and moxifloxacin) (ie, in whom the administration of the injections was completed within the time windows presented in Protocol 3.2 Trial Treatments [the duration of intravenous administration of OPC-61815 16 mg or 32 mg or placebo: 59 to

65 minutes] without interruption of administration from 30 minutes after the start, as well as the condition described in 7.4 Treatment Compliance) and for whom predose and postdose QT data are available for all 4 treatment periods.

For each OPC-61815 dose (16 mg and 32 mg), the upper limit of the CI for the time-matched difference in the least squares mean for the change in QTcF from baseline compared to the placebo data will be evaluated to determine if it is lower than 10 msec at all postdose time points using the hypothesis presented below. Because the alternative hypothesis is an intersection hypothesis, the 2-sided 90% CI (1-sided 95%) will be calculated without type 1 error adjustment.

$$H_0: \bigcup \{\mu_{A(i)} - \mu_{P(i)} \geq 10\}, i = 1, 2, \dots, 8$$

$$H_1: \bigcap \{\mu_{A(i)} - \mu_{P(i)} < 10\}, i = 1, 2, \dots, 8$$

$\mu_{A(i)}$: Mean change from baseline in QTcF interval at time i after OPC-61815 administration

$\mu_{P(i)}$: Mean change from baseline in QTcF interval at time i after placebo administration
 $i = 1, 2, \dots, 8$ respectively correspond to 1, 1.5, 2, 3, 4, 6, 12, and 24 hours after start of IMP administration

Using a linear mixed effect model with baseline QTcF in each treatment period as a covariate, treatment, sequence, treatment period, time point, and interaction between treatment and time point as fixed effects, and subject as a random effect, point estimates and CIs for the time-matched difference in the least squares mean for the change in QTcF from baseline compared to the placebo data will be calculated.

SAS code is shown below. The data set will include all 4 treatments data.

```
proc mixed method=reml;  
  class treatment subject time arm period;  
  model change = arm period treatment time treatment*time baseline/ s ddfm=satterth;  
  random subject(arm);  
  lsmeans treatment*time/diff pdiff cl alpha=0.1;  
run;
```

11.1.2 Secondary Endpoint Analysis

Analyses described in the subsequent sections will be performed per treatment in the pharmacodynamic analysis set.

11.1.2.1 Categorical Analysis

The number and percentage of subjects who fulfilled the following criteria for QTcF interval at least once after IMP administration are calculated. The same calculation will also be performed at 3 predose time points and each postdose time point for 1), and at each postdose time point for 2).

- 1) Prolongation of absolute QTc interval:
 - QTc interval > 450 msec
 - QTc interval > 480 msec
 - QTc interval > 500 msec
- 2) Change from baseline in QTc interval:
 - > 30 msec increase in QTc interval from baseline
 - > 60 msec increase in QTc interval from baseline

11.1.2.2 Electrocardiogram (12-lead Holter Electrocardiogram)

For each parameter (heart rate, RR interval, PR interval, QRS interval, QT interval, and QTcF interval), descriptive statistics will be calculated for measurements and changes from baseline at each time point.

A shift table of normal/abnormal assessments at each postdose time point compared to baseline will also be created. In a triplicate 12-lead ECG at each time point, an ECG parameter will be assessed as “normal” only when all 3 measurements are normal; otherwise it will be assessed as “abnormal” (ie, if any measurement is abnormal). In baseline assessment of 12-lead Holter ECGs at 3 predose time points (1 hour, 30 minutes, and 15 minutes before IMP administration) in each period, an ECG parameter will be assessed as “normal” only when all measurements at 3 predose time points are normal; otherwise it will be assessed as “abnormal” (ie, if any measurement is abnormal).

For the electrocardiographic waveform pattern, the number and percentage of subjects satisfying each Change Relative to Baseline at least once after IMP administration based on Criteria for Identifying ECG Measurements of Potential Clinical Relevance ([Appendix 1](#)) will be calculated. The same calculation will also be performed at each time point.

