3.7.5.6.2 Days 1 and 2 in Each Period and Post-treatment Follow-up

Resting 12-lead ECGs will be performed at the scheduled time points (see Table 3.7-1 and Table 3.7-2) using a well-maintained standard 12-lead electrocardiograph provided by the trial site or a 12-lead Holter electrocardiograph supplied by the central ECG laboratory according to the procedure specified by the trial site.

12-lead ECG will be performed once, not in triplicate, with electrodes placed at the same places at all time points wherever possible.

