6.2 Pharmacodynamic Methods

12-lead Holter ECG parameters will be analyzed at a central ECG laboratory. The central laboratory will obtain 3 snapshots for each scheduled ECG from the 12-lead Holter ECG data sent from the trial site, determine the ECG parameters (heart rate, RR interval, PR interval, QRS interval, QT interval, and QTcF interval), and assess waveform patterns. Time windows for data capture are presented in Table 6.2-1. Each data capture will be obtained at an interval of at least 1 minute. The mean from 3 captures will be recorded as the value for each ECG measurement.

Schedule for 12-lead Holter ECG Data Capture^a		Time Window
Day 1	1 hour before IMP administration	Within –5 minutes
	30 minutes before IMP administration	
	15 minutes before IMP administration	
	1 hour after start of IMP administration	Within 5 minutes before end of IMP administration ^b
	1.5 hours after start of IMP administration	Within –5 minutes
	2 hours after start of IMP administration	
	3 hours after start of IMP administration	
	4 hours after start of IMP administration	
	6 hours after start of IMP administration	
12 hours after start of IMP administration		
Day 2	24 hours after start of Day 1 IMP administration	

^a: For moxifloxacin, “IMP administration” instead of “start of IMP administration” in the above table

^b: “Within –5 minutes” for moxifloxacin

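### Does the Holter normal/abnormal shift table mislead because baseline is judged on up to nine snapshots and each postdose time point on three?

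*SAP*

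**What the plan says.** SAP 11.1.2.2 plans the table in one sentence: "A shift table of normal/abnormal assessments at each postdose time point compared to baseline will also be created". It then gives two rules. Within one time point recorded in triplicate, a parameter is normal "only when all 3 measurements are normal". For baseline, which pools the recordings at 1 hour, 30 minutes and 15 minutes before dosing, it is normal "only when all measurements at 3 predose time points are normal".

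Protocol 6.2 fixes the number of readings: "The central laboratory will obtain 3 snapshots for each scheduled ECG". The same section adds: "The mean from 3 captures will be recorded as the value for each ECG measurement".

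SAP 11.1.2 says that the secondary analyses, including this table, "will be performed per treatment in the pharmacodynamic analysis set". SAP 11.1.2.1 plans counts of absolute QTc above 450, 480 and 500 msec, listed there as item 1, and of increases above 30 and 60 msec. On timing it says "The same calculation will also be performed at 3 predose time points and each postdose time point for 1".

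**The concern.** The two sides of the table are judged on different numbers of readings. An any-abnormal rule over nine snapshots is met at least as often as the same rule over three. A parameter that is abnormal now and then, for reasons unrelated to treatment, is therefore more likely to be flagged at baseline than at any one postdose time point. Someone reading a single treatment's table could take the surplus of abnormal-to-normal shifts for improvement. Some new postdose abnormalities would also go uncounted as shifts, because the subject was already classed as abnormal at baseline. In a QT study, new abnormality after dosing is the direction that matters for safety. Section 11.1.2.2 neither tells the reader to use placebo as the reference nor sets out a version with equal numbers of readings.

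**Working it through.** **Which readings are meant.** Protocol 6.2 stores a mean of three captures, so one might ask whether a measurement in the SAP rule is that mean. It cannot be in the time-point rule, which needs three measurements at one time point. The standard safety ECG does not supply them either: on Days 1 and 2, Protocol 3.7.5.6.2 says "12-lead ECG will be performed once, not in triplicate". The three measurements are the Holter snapshots. Baseline has up to 3 × 3 = 9 and each postdose time point has 3.

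**Inputs.** There are 48 subjects (SAP Section 4). The plan states no figure for this table to reproduce, and no abnormality rate. I assume a rate p per snapshot of 0.5%, 1% or 5%, with no drug effect and no time-of-day drift.

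**Independent snapshots.**
- Normal to abnormal: (1−p)^9 × [1−(1−p)^3]
- Abnormal to normal: [1−(1−p)^9] × (1−p)^3
- Matched three-against-three, each way: (1−p)^3 × [1−(1−p)^3]

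At p = 1%, (0.99)^9 = 0.9135 and (0.99)^3 = 0.9703. Normal to abnormal is 0.9135 × 0.0297 = 0.0271, or 1.3 of 48. Abnormal to normal is 0.0865 × 0.9703 = 0.0839, or 4.0 of 48. Matched is 0.9703 × 0.0297 = 0.0288, or 1.4 of 48.

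**Correlated snapshots.** This is a threshold model on a latent scale, with 50% of the variance between subjects, 20% between time points and 30% between snapshots.

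Expected subjects of 48 at one postdose time point:

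| Rate | Snapshots | Normal to abnormal | Abnormal to normal | Matched, each way |
|---|---|---|---|---|
| 0.5% | independent | 0.7 | 2.1 | 0.7 |
| 1% | independent | 1.3 | 4.0 | 1.4 |
| 5% | independent | 4.3 | 15.2 | 5.9 |
| 0.5% | correlated | 0.4 | 1.3 | 0.5 |
| 1% | correlated | 0.6 | 2.2 | 0.9 |
| 5% | correlated | 1.8 | 7.1 | 3.1 |

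The ratio is about 3 to 4 throughout. The correlated rows are the more believable, because the three snapshots come from one five-minute supine window.

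**Against placebo.** Within a treatment, normal-to-abnormal minus abnormal-to-normal equals P(postdose abnormal) − P(baseline abnormal). The baseline term has the same expectation under drug and placebo, since both use the same nine-snapshot rule before dosing. It drops out of the drug-minus-placebo difference, whatever the correlation. Example, correlated model at 5% with an assumed drug shift of 0.5 latent SD: the net difference is 12.9 percentage points under both nine-against-three and three-against-three.

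The one-way count does not cancel completely. In that example the drug-minus-placebo excess of normal-to-abnormal shifts is 7.6 points under the planned rule and 10.4 under the matched rule. The gap is 2.8 points, or 0.028 × 48 = 1.3 subjects. At a 2% rate the figures are 5.3 and 6.6 points, a gap of 1.3 points or 0.013 × 48 = 0.6 subjects.

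**The case for a change.** The best case for acting is that cancellation against placebo is only partial. A reader who looks at normal-to-abnormal shifts alone, even beside placebo, sees a somewhat diluted drug signal. The SAP does not direct the reader to the placebo table, and a repair would be cheap: a footnote, plus a display of the percentage abnormal at each predose and postdose time point by the same three-snapshot rule. SAP 11.1.2.1 already uses that layout for the absolute QTc thresholds.

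The dilution stands, but its size depends on assumed rates and an assumed drug shift. With no drug effect and correlated snapshots, the normal-to-abnormal shifts lost at rates of 0.5% to 1% are about 0.1 to 0.2 of 48 subjects. A matched table would still need placebo as its reference, because Protocol 3.1 itself recognises circadian ECG variation, and such drift could add to the lean or offset it. For QTcF, the parameter the trial is about, the threshold counts already give a view that does not use this baseline rule, and descriptive statistics are planned for every Holter parameter at each time point. Whether a matched display is already planned cannot be settled here, because SAP Appendix 2, the list of summary tables, is not in the text available. What remains is an optional presentational extra for the non-QTcF parameters.

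**Conclusion.** No change is needed. The nine-against-three imbalance is real, and its direction holds for any correlation between exchangeable snapshots; the two rules agree only if the snapshots always agree. Under the assumed rates of 0.5% to 5%, with no drug effect and no drift, the planned rule gives 0.4 to 4.3 normal-to-abnormal shifts per time point among 48 subjects, against 1.3 to 15.2 the other way. Compared with a matched rule, it loses 0.02 to 1.6 normal-to-abnormal shifts.

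This is a fair trade-off. A wide baseline net avoids calling an abnormality new when it was already present before dosing, and the cost is some sensitivity in a descriptive table. The table is produced for placebo under the same rule in a crossover, so the natural comparison removes the net lean. It enters no test and no decision. The primary QTcF analysis, the moxifloxacin assay-sensitivity assessment, the QTcF threshold counts and the sample size do not use the rule. An analyst may add a note to read the shifts beside placebo, but its absence alters nothing the trial can conclude.

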11.1.3 Assay Sensitivity Assessment

As an assay sensitivity assessment, moxifloxacin will be evaluated as a positive control using the same analysis set, data set, and statistical method as those stated in 11.1.1 Primary Endpoint Analyses.

For moxifloxacin, the lower limit of the CI for the time-matched difference in the least squares mean for the change in QTcF from baseline compared to the placebo data will be evaluated if it is higher than 0 msec at any of the postdose time points using the hypothesis presented below. Because of the multiplicity arising from assay sensitivity assessments at 5 postdose time points (1, 1.5, 2, 3, and 4 hours), type 1 error adjustment will be performed using the Bonferroni method, and the 2-sided 98% (1-sided 99%) CI will be calculated (alpha = 0.02 in SAS code in 11.1.1 Primary Endpoint Analyses).

$$H_0: \bigcap \{ \mu_{M(i)} - \mu_{P(i)} \leq 0 \}, i = 1, 2, \dots, 5$$

$$H_1: \bigcup \{ \mu_{M(i)} - \mu_{P(i)} > 0 \}, i = 1, 2, \dots, 5$$

$\mu_{M(i)}$: Mean change from baseline in QTcF interval at time i after moxifloxacin administration

$\mu_{P(i)}$: Mean change from baseline in QTcF interval at time i after placebo administration

$i = 1, 2, \dots, 5$ respectively correspond to 1, 1.5, 2, 3, and 4 hours after IMP administration

12 Pharmacogenomic Analyses

No pharmacogenomic analysis will be performed.

13 Interim Analysis

No interim analysis will be performed.

14 Changes in Planned Analysis

- For omission in entry, "V_z/BW" was added in Protocol 6.1.2 (1) Endpoints.
- For erroneous entry, "Apparent" in the definition of "V_z" in the Pharmacokinetics Parameter Table was deleted.

Protocol 263-102-00005

15 References

None.
